**1 OBJECTIVES:**

**Aim 1:** Assess the feasibility of continuous long-term monitoring of patients with stroke using wearable sensors.

We will obtain quantitative health data from research-grade, wireless, wearable sensors on individuals with subacute and chronic stroke in the clinical setting, as well as healthy controls.

We will specifically check for variability in device data, as well as consistency and periodicity of sensor readings across the clinical study period. We will analyze test-retest reliability and inter-rater reliability of using the wearable sensor technology for clinical and monitoring applications. Furthermore, we will determine whether the sensors can distinguish biometric and activity characteristics between healthy controls and individuals with stroke.

**Aim 2:** Quantify upper and lower extremity movement impairments, mobility-related activities, speech and swallowing activities, and clinical parameters during stroke recovery.

We will obtain continuous biometric and movement-based sensor data for clinical symptoms (e.g., muscle activation, heart rate variability, talk time, gait quality, and balance) during the performance of validated clinical tests and during general clinical activities (e.g., therapy, eating, and sleeping).

We will compare device data with clinically validated measures of movement and language function, such as the Modified Ashworth Scale or Western Aphasia Battery. We will describe variation of device data in subgroups of subjects defined by clinician assessed clinically validated measures (10-Meter Walk Test, Mini-Mental Status Exam, etc.). We will also assess the ability of the sensors to capture response to treatment, such as movement therapy, speech therapy, medication, and Botox by comparing sensor data before and after treatment. We will provide evidence about the degree to which the measured variables are intercorrelated. Lastly, we will evaluate and compare the state of recovery between patients at time of discharge using

STU#: STU00205532

sensor-based outcomes. Due to heterogeneity of clinical symptoms after stroke, as differing etiologies and degrees of recovery result in different types and levels of gait impairments, preliminary analyses may be performed on specific sub-datasets to determine which predictors, data types, and other data compositions affect algorithm performance before their application and evaluation on the dataset collected at the end of this study. Sub-datasets may be sampled based on (but not limited to) the population characteristics, the sensors used, the data available at the time analysis.

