## 4 STUDY-WIDE NUMBER OF PARTICIPANTS:

The exploratory phase of the study will enroll up to 100 subjects as healthy controls, assuming 10% attrition. The study will enroll up to 400 subjects with subacute and chronic stroke for the clinical monitoring at the Shirley Ryan AbilityLab (SRAlab), assuming 50% attrition.

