## 5 STUDY TIMELINES:

Inpatients with stroke will undergo up to **four types of assessment** (clinical, swallowing/speech, exercise, and sleep/rest) during inpatient stay, from the time of consent until discharge from the hospital or dropout from the study. **Assessments will be completed a minimum of two times**, including: (1) upon consent (surrounding admission to hospital), and

STU#: STU00205532

(2) at discharge. Assessments will be completed at additional times as schedules allow. Additional visits to monitor stroke recovery over time may be completed at 5 different time points following discharge from inpatient rehabilitation.

Individuals from the community who had a stroke and healthy controls will undergo up to **three types of assessment** (clinical, swallowing/speech, and exercise) **during up to 5 laboratory visits** (expected 2-3 hours). Additional visits may be necessary if technical issues arise or sensor technology changes.

The assessments and their frequency for each cohort are as follows:

Assessment	# times (stroke)	# times (healthy)	Time required for each assessment
Clinical	2-10	5	1-2 hours
Swallowing/Speech	2-10	5	≤ 1 hour
Exercise	2-10	5	1 hour
Sleep and Rest	2-10	0	≤ 1 hours per day for rest, overnight for sleep (until wake)

Procedures for each assessment are described in Section 6.2 (individuals with stroke - inpatient) and 6.3 (chronic stroke and healthy controls).

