## 6 PROCEDURES INVOLVED:

### 6.1 Overview and Scope

Sensors can collect the following data from healthy controls and patients with stroke:

- Biometric data, including electrocardiography (ECG), electromyography (EMG), and sweat.
- Movement data from the limbs, including signals from triaxial accelerometers (ACC), gyroscopes (GYR), and magnetometer (MAG).
- Acoustomechanic laryngeal data to detect speech and swallowing events.

The sensors to be used will include commercial wearable devices as well as custom sensors designed by our collaborators, the [name] research group at Northwestern University. Both commercial and custom devices measure combinations of ACC, GYR, MAG, EMG, and ECG, ECG, while the custom sensors measure acoustomechanic laryngeal data and sweat.

Most of these sensors have been previously validated against gold standard measures for healthy controls and individuals with stroke (Table 1). Thus, feasibility of inpatient monitoring (**Aim 1**) will focus on validating these sensors during common clinical tests and mobility-related activities for healthy controls and subjects with stroke.

STU#: STU00205532

Quantification of stroke recovery (**Aim 2**) will involve the development of algorithms to analyze sensor data for healthy and stroke cohorts.

**Table 1.** Validation of wearable sensors (Commercial and custom sensors)

Sensor	Gold standard	Validation	Methods
EMG (250-1000 Hz)	Delsys (2000 Hz)	
SRAlab: Pilot study – similar SNR during plantarflexion MVC for 1 healthy subject at gastrocnemius (GA). Qualitatively similar signal profile during 10MWT for 1 healthy subject at tibialis anterior (TA). Temporal displacement of spikes possibly due to sensor's non-uniform sampling interval
 
SRAlab: In progress (data collected) – 9 healthy subjects and 8 with stroke
	MVC, sensor at GA  10MWT, sensor at TA
ACC (25-500 Hz)	Delsys (148.14 Hz)	
SRAlab: Pilot study – at GA, good correlation with Delsys norms during 10MWT for 2 subjects with stroke.
 
SRAlab: In progress (data collected) – 9 healthy subjects and 8 with stroke
	10MWT, sensor at GA.
GYR (25-500 Hz)	ActiLink GT3X (100 Hz)	
SRAlab: In progress (data collected) – 9 healthy subjects
 
No data for stroke (expected unnecessary: healthy subjects should be sufficient to validate angular velocity at same sampling frequency as GT3X)
	N/A

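### Aim 1 asks whether long-term monitoring is feasible, but every measure it names is computed on recorded signals, so refusals, dropouts and failed recordings cannot lower the result

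*Protocol*

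**What the plan says.** Section 1 states the objective of Aim 1: "Assess the feasibility of continuous long-term monitoring of patients with stroke using wearable sensors". It then lists what will be examined:

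- Signal behaviour: "We will specifically check for variability in device data, as well as consistency and periodicity of sensor readings across the clinical study period".
- Reliability: "We will analyze test-retest reliability and inter-rater reliability of using the wearable sensor technology for clinical and monitoring applications".
- Discrimination: "we will determine whether the sensors can distinguish biometric and activity characteristics between healthy controls and individuals with stroke".

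Section 6.1 links feasibility to sensor performance. It says that feasibility of inpatient monitoring under Aim 1 "will focus on validating these sensors during common clinical tests and mobility-related activities for healthy controls and subjects with stroke".

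Loss of participants appears in Section 4 as an enrolment assumption: up to 400 stroke participants, "assuming 50% attrition", and up to 100 healthy controls with 10% attrition. Section 16 repeats the rates but gives up to 300 stroke participants. Section 10 allows data gathered before a participant discontinues to be used. It does not make discontinuation an outcome.

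On timing, Section 5 gives inpatients at least two assessment occasions, at consent and at discharge, and adds: "Assessments will be completed at additional times as schedules allow". In the next paragraph, on community stroke and healthy participants, it says: "Additional visits may be necessary if technical issues arise or sensor technology changes".

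**The concern.** Feasibility of long-term monitoring depends partly on whether people accept the sensors, stay in the study and yield a usable recording when one is planned. The measures named for Aim 1 describe how good the signal is once it exists. They leave out the people and sessions for which there is none.

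Sensors could therefore give stable, reliable and discriminating signals in those who stayed, and Aim 1 could be reported as met, while a large share of consented stroke patients never supplied the planned data. Clinicians reading such a result would take it as evidence that the system can be used on a ward. The evidence would in fact be conditional on the recording having worked.

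**Working it through.** The protocol gives no feasibility threshold, completion target or power calculation, so there is no stated figure to reproduce. The check has two parts.

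**1. Can each named measure register a missing recording?**

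| Measure (Sections 1 and 6.1) | Data it needs | Effect of a refusal, dropout or failed session |
|---|---|---|
| Variability, consistency, periodicity | Recorded readings | None; at most, consistency over time may show gaps inside one wearer's record |
| Test-retest and inter-rater reliability | At least two readings to compare | None; a person with only one reading is left out |
| Stroke versus healthy discrimination | Recorded readings in both groups | None |
| Sensor validation during tests and activities | Sensor and reference data | None |

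No measure has consented participants or planned sessions as its denominator. The staff logs (Sections 6.2.C and 6.2.E) are kept while assessments take place and are consulted for comparison with timestamped sensor data. They are not described as counting sessions that did not happen.

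**2. How large could the unregistered loss be?**

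Inputs from Sections 4 and 16: enrolment ceiling N and attrition d. Completers = N × (1 − d).

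- Stroke, Section 4: 400 × (1 − 0.50) = 200.
- Stroke, Section 16: 300 × (1 − 0.50) = 150.
- Healthy controls: 100 × (1 − 0.10) = 90.

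Let s be the share of completers who give usable data. The protocol does not state s; I assume 0.80 to 1.00. Usable share of all enrolled = s × (1 − d).

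- Stroke: 0.80 × 0.50 = 0.40, to 1.00 × 0.50 = 0.50.
- Healthy: 0.80 × 0.90 = 0.72, to 1.00 × 0.90 = 0.90.

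On the protocol's own attrition rates, completion would thus be 40-50% of enrolled stroke participants against 72-90% of controls. The Aim 1 measures would show neither the level nor the difference.

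**The case against.** The strongest reply is that the protocol declares what it means by feasibility. Section 6.1 equates it with sensor validation, and asking for a completion measure is asking for a different construct. Denominators, missing-session rules and the definition of a usable recording often belong in the SAP, which is not at hand. No stated figure is wrong. Part of this stands: no sentence says that failures are excluded, so their absence from the result is inferred from the measures listed. But the protocol does more than stay silent. It poses a question about continuous long-term monitoring and then names measures that cannot answer it. An SAP would have to add to that definition, not just fill in its detail.

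Three stronger readings are tempting, and the documents do not support them.

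- *Repeat visits hide technical failures throughout the study.* The sentence on additional visits for technical issues concerns community stroke and healthy participants. Extra inpatient assessments depend on schedules and are not tied to failure. Nor does the protocol say that a repeat replaces the failed session.
- *Most planned recordings would never take place.* Suppose that a session succeeds with probability p, and that all 50% attrition falls between the two minimum inpatient occasions. The completed share is then (p + 0.5p)/2 = 0.75p. For an assumed p of 0.70, 0.85 or 0.95, this is 52.5%, 63.75% or 71.25%, a majority each time. The timing is itself an assumption: the attrition figure is undated, covers subacute and chronic stroke together, and could include optional visits after discharge.
- *The activity logs already hold the count.* They cover sessions that took place, so the enrolment list and the schedule are needed too.

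It is also fair to say that counting every dropout as a failure would charge medical events and investigator-decided withdrawals (Section 10) to the sensors. Reporting by reason answers this.

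**Conclusion.** The point holds in this form: Aim 1 is framed as feasibility but measured only through recorded signals, so refusals, dropouts and failed recordings cannot lower any of its measures. The mismatch follows from Sections 1 and 6.1 alone and needs no assumption.

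Its possible size rests on the protocol's 50% attrition (at most 200 of 400 stroke completers, or 150 of 300) and, for the 40-50% figure, on an assumed 80-100% of completers with usable data. The two enrolment ceilings, both given for the same site, should be reconciled.

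This does not invalidate the signal analyses, which answer a proper question about sensor performance. It limits what may be concluded about feasibility, and should be corrected before Aim 1 is reported.

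**What to change.** Add one feasibility measure to Aim 1, reported by assessment type and cohort: usable first-attempt recordings divided by planned recordings, in all consented participants.

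- **Denominator, inpatients:** the two minimum occasions in Section 5 (consent and discharge) for each assessment type assigned to the participant. Extra assessments held as schedules allow stay outside it.
- **Denominator, community stroke and healthy participants:** the visits scheduled at enrolment. This must be recorded then, because Section 5 sets only an upper limit on visits.
- **Numerator:** usable recordings at the first attempt, with usable defined in advance for each assessment type.
- **Non-completion:** count it as not achieved and give the reason: refusal, withdrawal or medical event, or technical failure.
- **Additional visits for technical issues** (community stroke and healthy participants): report them separately. Their data feed the signal analyses but do not replace the failed first attempt in the count.
- **Sources:** the enrolment list and visit schedule, together with the staff logs.

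No participant undergoes anything new, and the planned signal analyses are unchanged. The costs are some added tracking of planned sessions and reasons for non-completion, and a feasibility figure that will look less favourable.

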## 7 DATA COLLECTION AND ANALYSIS

Healthy controls and individuals with stroke will be instrumented with wireless sensors. Data from participants will be collected to validate sensor signals and clinical outcomes. Data from inpatients will be collected during hospital stay, including clinical, swallowing, exercise, and sleep/rest assessments. For all subjects, biometric information will be derived using sensor-based electrocardiography, electromyography, and accelerometry. Movement of the upper and lower limbs will be detected as changes in the acceleration, gyroscope, and magnetometer values in three axes. Speech and swallowing activities will be detected as changes in the acoustical waveform obtained from the laryngeal sensor. Clinical scores and therapist evaluations will be incorporated to further validate sensor-based outcomes and map these outcomes onto traditional measures of stroke recovery.

The complete medical history of the inpatients, including physical findings, radiological reports such lesion size, location, type, medications and therapist-assessed clinical outcomes may be used to associate with biometric and movement obtained from the wearable sensors.

Subjects' records will be kept completely confidential. Data will be collected and kept confidential and compliant with HIPPA requirements. Research data will be de-identified and stored in locked cabinets in the lab with access only to research staff. Electronic data will be de-identified and kept on secure, password protected files and password protected computers (see Sec. 7 for details).

We will use kinematic models to estimate gait-based parameters (such as step duration or joint angles) and physiological models to estimate cardiac parameters (such as MET intensities or time in target heart rate zone). We will use machine learning techniques for activity recognition, classifying different mobility-related activities (such as walking or stair use). We will also use traditional multiple correlation and regression analysis to identify associations of clinical outcomes with measures of body structure and function, activity limitations and demographic characteristics. Analysis will be performed in subsets of the stroke cohort and also in comparison with the healthy controls. This will guide us the ability to create clinical predictors for recovery following stroke and measure the state of recovery prior to hospital discharge.

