## **9 DATA AND SPECIMEN MANAGEMENT:**

We will use kinematic models to estimate gait-based parameters (such as step duration or joint angles) and physiological models to estimate cardiac parameters (such as MET intensities or time in target heart rate zone). We will use machine learning techniques for activity recognition, classifying different mobility-related activities (such as walking or stair use) and swallowing/speech events. We will also use traditional multiple correlation and regression analysis to identify associations of clinical outcomes with measures of body structure and function, activity limitations and demographic characteristics. Analysis will be performed in subsets of the stroke cohort and also in comparison with the healthy controls. This will guide us the ability to create clinical predictors for recovery following stroke and measure the state of recovery prior to hospital discharge.

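### Protocol section 1 (Aim 2) permits predictors to be chosen on early sub-datasets of the study's own data and does not keep those participants out of the final evaluation, so reported performance can be optimistic

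*Protocol*

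**What the plan says.** The last part of Aim 2 (Protocol section 1) notes how heterogeneous stroke is and says that "preliminary analyses may be performed on specific sub-datasets". The purpose is to find "which predictors, data types, and other data compositions affect algorithm performance before their application and evaluation on the dataset collected at the end" of the study. Sub-datasets may be drawn by population, by sensor or by "the data available at the time analysis", and this list is expressly not exhaustive.

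Four other places bear on the point:

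- Section 6.1 says that Aim 2 "will involve the development of algorithms to analyze sensor data for healthy and stroke cohorts".
- Section 7 gives the intended product: to "create clinical predictors for recovery following stroke and measure the state of recovery prior to hospital discharge". Section 9 repeats this.
- Sections 7 and 9 name machine learning and regression. Neither says which participants train a model and which test it.
- Section 5 says of inpatients: "Assessments will be completed a minimum of two times". It also allows optional visits after discharge, so one person can supply both early and late records.

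**The concern.** The protocol separates a preliminary step from a final evaluation. That separation protects the result only if the people in the evaluation did not help to choose what is being evaluated. The text does not secure this. The sub-datasets are most naturally read as cuts of this study's accruing data, and the end-of-study dataset as everything accumulated by then.

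Cross-validating the final model does not repair the overlap. If a predictor was kept because it happened to fit the early participants' outcomes, those outcomes have already influenced the model before the folds are formed. Each test fold then contains people for whom the predictor was chosen.

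At stake is the accuracy reported for the recovery predictors, which is a main result of Aim 2. Timing also matters: unless someone records who was used early, a clean set of unused participants may not be recoverable later.

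**Working it through.** **Step 1: what the final dataset could mean.** The protocol states no performance figure, split or candidate count, so there is nothing to reproduce. Three readings are open:

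1. All data accumulated by the end. Selection participants are then also in the evaluation, and bias is possible.
2. Only participants enrolled after the preliminary work. There is then no bias from this source.
3. Only later records, some from people already used. The result then depends on how alike a person's records are (Step 5).

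**Step 2: inputs for an illustration of reading 1.**

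- Section 16: up to 300 with stroke, 50% attrition: 300 × 0.5 = 150.
- Section 4: up to 400 with stroke, 50% attrition: 400 × 0.5 = 200.
- Section 10 lets data collected before withdrawal be used, so up to 400 could contribute.
- Assumed, because the protocol does not give them: p = 20, 50 or 200 candidate features; half of the participants used early; the 10 features most correlated with the outcome kept; normal features, independent or in blocks of 10 with a common correlation. Section 1 promises "evidence about the degree to which the measured variables are intercorrelated" but gives no value.

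**Step 3: the mechanism by hand (N = 200, p = 200, independent features, no true signal).**

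- Early participants: 0.5 × 200 = 100. A null correlation has a standard error of about 1/√100 = 0.10.
- Share kept: 10/200 = 5%, that is, roughly those with |z| > 1.96.
- Mean |z| among those kept: 2φ(1.96)/0.05 = 2 × 0.0584/0.05 = 2.34. Mean early |r| is therefore about 0.10 × 2.34 = 0.23.
- The unused half adds zero on average, so the full-sample correlation is about 0.5 × 0.23 = 0.12 for each of ten pure-noise predictors.

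Cross-validation on all 200 treats these chance correlations as signal.

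**Step 4: simulation of reading 1.** Select on the first half of the participants, fit least squares, and run 5-fold cross-validation by participant on all N. Report r between predicted and observed outcome. There is no true signal, so an honest r is about 0.

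| Block correlation | p=20, N=150-200 | p=50, N=150-200 | p=200, N=150-200 | p=200, N=400 |
|---|---|---|---|---|
| 0 | 0.04-0.05 | 0.12-0.14 | 0.21-0.23 | 0.16 |
| 0.5 | about 0 | 0.05 | 0.15-0.17 | 0.11 |
| 0.7 | below 0 | 0.00-0.01 | 0.10-0.11 | 0.07-0.08 |
| 0.9 | below 0 | below 0 | 0.03-0.04 | 0.02-0.03 |

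Other settings at N = 150-200:

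- Five candidates, two kept: no inflation (r from -0.08 to 0.00).
- p = 200, independent features: 0.11-0.12 if a quarter is used early, 0.30-0.33 if three quarters are.
- Real signal (joint R² = 0.2), half used early, p = 200: reported minus true r is 0.14-0.18 for independent features and 0.02-0.03 at block correlation 0.9.
- Selection repeated inside each training fold: r from -0.04 to -0.01.
- Evaluation only on participants never used early: within 0.01 of 0.

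**Step 5: reading 3 (two records per person, no true signal, half used early, block correlation 0 to 0.7).**

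- If only the choice of predictors carries over, r is -0.04 to -0.01 for within-person correlation up to 0.5, at most 0.05 at 0.7, and at most 0.16 at 0.9.
- If models are also fitted on those people's earlier records, r is 0.03-0.07, 0.07-0.19, 0.15-0.35 and 0.27-0.57 at within-person correlation 0.3, 0.5, 0.7 and 0.9. Section 1 does not describe such fitting.

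**The case against.** The strongest reply is that data splits, fold construction and nesting usually belong in a statistical analysis plan, which may exist and is not at hand. Nothing in section 1 says that the same people will select and score. This stands in part: missing cross-validation detail alone would be no finding. But the protocol itself authorises data-driven selection ahead of the evaluation and leaves the evaluation set open. A plan that only cross-validated the final model would inherit the problem.

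Other replies stand as limits:

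- The step is optional, and one reading of the final dataset is harmless.
- Keeping the ten best-correlated features is an assumption. Section 1 does not state a selection rule, and comparing a few sensors or data types involves few candidates.
- The machine-learning uses that the protocol names are activity recognition and, in section 9, "classifying different mobility-related activities (such as walking or stair use) and swallowing/speech events". The illustration covers participant-level regression and does not size bias for event-level classification.
- Sensors may change during the study (sections 5, 6.2.B and 6.3.B), so selection among them cannot always be repeated.

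A reader might infer that the plan does reuse the same participants, or that its results will be inflated by a known amount. The documents support neither. Overlap is permitted, not stated, and the inputs that determine its effect are not given.

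**Conclusion.** The point holds as an ambiguity that permits bias, and it should be closed. If the final dataset is the full dataset and selection is driven by outcomes, reported performance can be optimistic. The size depends on the number of candidates, their correlation and the share used early, none of which the protocol gives. At N = 150 to 400 with half used early, the illustration spans no inflation to a spurious r of about 0.16-0.23, and that upper end needs 200 independent candidates. Larger values arise only under further assumptions, such as three quarters used early or fitting on the same people's earlier records. Confidence is medium, because the full-dataset reading is the natural one but not the only one.

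**What to change.** In section 1, Aim 2, define the end-of-study dataset: all participants, or only those enrolled after the preliminary analyses. Then add text to this effect:

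*Every participant whose data enter a preliminary analysis will be flagged. Final algorithm performance will be estimated either (a) only on participants never used in a preliminary analysis, or (b) by cross-validation with folds formed by participant and all outcome-driven selection repeated inside each training fold, among candidates actually recorded for the participants analysed. Where selection cannot be repeated, for example because a sensor was dropped or changed, option (a) will be used or the result will be reported as exploratory. The option will be fixed before the final dataset is analysed.*

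The cost is a few sentences and one flag per participant. Option (a) leaves a smaller test set; option (b) takes more analysis work. Reported accuracy is likely to be less favourable under either. If only newly enrolled participants were meant, one sentence saying so settles the point.
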